	

• Age <math>\geq</math> 18 years

• Karnofsky performance score <math>\geq</math> 60 (Eastern Cooperative Oncology Group [ECOG] performance score of 0, 1, or 2)

• Histologically confirmed diagnosis of B-cell iNHL, with histological subtype limited to the following based on criteria established by the World Health Organization (WHO) 2008 classification of tumors of haematopoietic and lymphoid tissues:

— Follicular lymphoma (FL) Grade 1, 2, or 3a

— Small lymphocytic lymphoma (SLL) with absolute lymphocyte count <math><5 \times 10^9/L</math> at the time of diagnosis and on baseline laboratory assessment performed within 4 weeks prior to the start of study drug administration

— Lymphoplasmacytic lymphoma/Waldenstrom Macroglobulinemia (LPL/WM)

— Marginal zone lymphoma (MZL) (splenic, nodal, or extra-nodal)

• Histological materials documenting diagnosis of lymphoma available for review. Note: Central pathology confirmation of diagnosis will be performed in this study. However, a subject may be enrolled without waiting for confirmation of histological diagnosis on condition that pathological materials are known to be available for review.

• Presence of radiographically measurable lymphadenopathy or extranodal lymphoid malignancy (defined as the presence of <math>\geq 1</math> lesion that measures <math>\geq 2.0</math> cm in the longest dimension [LD] and <math>\geq 1.0</math> cm in the longest perpendicular dimension [LPD] as assessed by <math>\geq</math> CT or magnetic resonance imaging [MRI])

• Prior treatment with <math>\geq 2</math> chemotherapy- or immunotherapy-based regimens, or with rituximab/with an alkylating agent for iNHL

• Prior treatment with rituximab and with an alkylating agent (eg, bendamustine, cyclophosphamide, ifosfamide, chlorambucil, melphalan, busulfan, nitrosoureas) for iNHL.

• Lymphoma that is refractory to rituximab and to an alkylating agent

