### Schedule of Assessments

Period	Screen	Treatment															Follow-up		
Visit	1	2	3	4	5	6	7	8	9	10	11	12	13	14	15	16+	End of Treatment	Immediate post-treatment	Long-term
Week	-4	0	2	4	6	8	10	12	16	20	24	30	36	42	48	Q12 Weeks			
Study Day	Within -28 Days	1	15	29	43	57	71	85	113	141	169	211	253	295	337				
Visit Window		±2	±2	±2	±2	±2	±2	±2	±3	±3	±3	±3	±3	±7	±7	±7			
Informed consent	X																		
Medical history	X																		
Histopathology review	X																		
Serum virology	X																		
Coagulation	X																		
Urinalysis	X																		
β-HCG	X																		
PPD																			
HRQL – FACT-Lym		X		X		X		X	X	X	X	X	X	X	X				
Study drug return/accounting			X		X		X	X	X	X		X		X	X	X			
Adverse events		X		X		X		X	X	X	X	X	X	X	X	X	X		
Concomitant medications	X	X		X		X		X	X	X	X	X	X	X	X	X			
Performance status	X	X		X		X		X	X	X	X	X	X	X	X	X			
Vital signs	X	X		X		X		X	X	X	X	X	X	X	X	X			
Hematology	X	X	X	X	X	X	X	X	X	X	X	X	X	X	X	X			
Serum chemistry	X	X	X	X	X	X	X	X	X	X	X	X	X	X	X	X			
Pharmacodynamics		X		X		X		X	X	X	X	X	X	X	X	X			
Drug dispensing		X		X		X		X	X	X	X	X	X	X	X	X			

Period	Screen	Treatment																Follow-up		
		1	2	3	4	5	6	7	8	9	10	11	12	13	14	15	16+	Q12 Weeks	End of Treatment	Imme- di- ate post- treat- ment
Visit	1																			
Week	-4	0	2	4	6	8	10	12	16	20	24	30	36	42	48					
Study Day	Within -28 Days	1	15	29	43	57	71	85	113	141	169	211	253	295	337					
Visit Window			±2	±2	±2	±2	±2	±2	±3	±3	±3	±3	±3	±7	±7	±7				
Physical examination	X								X									X		
12-lead ECG	X								X									X		
Immunophenotyping		X				X			X		X		X		X	X	X			
Serum immunoglobulins		X				X			X		X		X		X	X	X			
Radiology assessments (CT/MRI)	X					X			X		X		X		X	X	X			
Bone marrow biopsy/aspirate a	X					X a			X a		X a		X a		X a	X a				
SPEP (IgM monoclonal protein)	X					X			X		X		X		X	X	X			
Idelalisib dosing in clinic		X		X		X			X											
Limited PK		X		X		X			X											
PPD																				

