#### Study Procedures and Timingc

a Required at screening. If disease present at baseline, to be performed post-baseline to confirm response category in subjects with potential CR by radiological assessments. If the baseline bone marrow biopsy/aspirate does not show lymphoma involvement, it is not necessary to obtain a follow-up bone marrow biopsy/aspirate to establish CR.

b For subjects with LPL only, performed locally per standard of care

c For detailed information regarding activities to be performed at each visit, see Section 7.2 of study 101-09 protocol.

**Abbreviations:** β-HCG, beta human chorionic gonadotropin; HRQL, health-related quality of life; FACT-Lym, Functional Assessment of Cancer Therapy- Lymphoma; ECG, electrocardiogram; CT, computed tomography; LPL, lymphoplasmacytoid lymphoma; MRI, magnetic resonance imaging; SPEP, serum protein electrophoresis; CR, complete response

Randomization	No randomization will be performed in the study.
Site and/or Stratum Enrollment Limits	
Study subjects will be enrolled at investigational sites in North America and Europe.
 
At least 50 subjects with prior bendamustine exposure will be enrolled. The IWRS will gate accrual of subjects without prior bendamustine treatment.

Study Duration	
All subjects may receive study drug indefinitely unless any of the withdrawal criteria (such as withdrawal of consent, experienced an adverse event, or tumor progression) indicated in Section 9 of the protocol is met.
 
Subjects will be followed in the clinic at 2-week intervals through the first 12 weeks of treatment, at 4-week intervals from 12 to 24 weeks of treatment, at 6-week intervals from 24 to 48 weeks of treatment, and at 12-week intervals thereafter. Tumor response will be evaluated at baseline; at 8, 16, and 24 weeks of therapy; and every 12 weeks thereafter according to standard criteria. The responses will be assessed by both the investigator and an independent review committee (IRC), with the IRC-reviewed responses treated as primary in the efficacy analyses.
 
Enrollment is planned to occur over <math>\leq</math> 15 months; subject follow-up will continue through <math>\geq</math> 6 months.

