### **3. GENERAL CONSIDERATIONS FOR DATA ANALYSES**

#### **3.1. Analysis Sets**

##### **3.1.1. Intent-to-Treat Analysis Set**

The intent-to-treat (ITT) analysis set will comprise all subjects who receive  $\geq 1$  dose of IDELA. The ITT analysis set will be used in the analyses of ORR, progression-free survival (PFS), overall survival (OS), safety, and study drug administration and compliance. The ITT analysis set will be the primary analysis set for all the efficacy variables.

Duration of response (DOR) and time-to-response (TTR) will be analyzed based on all ITT subjects who achieve a CR or PR (including MR for subjects with WM). Lymph node response rate (LNR) will be analyzed based on all ITT subjects who have both baseline and  $\geq 1$  evaluable post-baseline tumor assessments.

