### **3.7. Data Handling Conventions and Transformations**

- By-subject listings will be presented for subjects in the ITT analysis set and sorted by subject number, visit, and time (if applicable).
- Summary tables for continuous variables will contain the following statistics: N (number in analysis set), n (number with data), mean, standard deviation (StD), 95% CI, median, Q1, Q3, minimum, and maximum. The same number of decimal places as in the raw data will be presented when reporting minimum and maximum, 1 more decimal place than in the raw data will be presented when reporting mean, median, Q1 and Q3, and 2 more decimal places than in the raw data will be presented when reporting StD and 95% CI.
- Summary tables for categorical variables for baseline and safety data will include: N, n, percentage. The tables for efficacy endpoints will include standard error, and 95% CIs on the percentage, where appropriate. Unless otherwise indicated, 95% CIs for binary variables will be calculated using the binomial distribution. The denominator for the percentages will be the number of subjects in the respective analysis set, unless otherwise specified. Missing data will be included as a row in tables where it is appropriate. All percentages will be presented as one-decimal point, unless otherwise specified. Percents equal to 100 will be presented as 100% and percents will not be presented for zero frequencies.
- Data from all sites will be pooled for all analyses.
- Unscheduled visits will only be included in listings and the best or worst post-baseline summary. Unscheduled visits will not be included in the by-visit summary tables, unless otherwise specified.

- Unless otherwise specified, all analyses will be 2-sided at the 0.05 level of significance.
- For Kaplan-Meier (KM) estimates, the 95% CIs will be calculated using Greenwood's formula with (complementary) log-log transformation.

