### **7.2.1. Summaries of Numeric Laboratory Results**

Descriptive statistics (sample size, mean, standard deviation, median, Q1, Q3, minimum and maximum) will be provided for each laboratory test specified in the study protocol as follows:

- Baseline values
- Values at each post-baseline analysis window
- Change from baseline at each post-baseline analysis window

In the case of multiple values in an analysis window, data will be selected for analysis as described in Section 3.8.3. In addition, the mean change from baseline for lab parameters will be plotted over time.

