3.2.1.1	Hematology: Summary of Actual Values and Change from Baseline	ITT Analysis Set
3.2.1.2	Hematology: Summary by Treatment-Emergent CTCAE Severity Grade	ITT Analysis Set

Table Number	Title	Analysis Set
3.2.1.3	Hematology: Shift from Baseline by CTCAE Severity Grade	ITT Analysis Set
3.2.2.1	Serum Chemistry: Summary of Actual Values and Change from Baseline	ITT Analysis Set
3.2.2.2	Serum Chemistry: Summary by Treatment-Emergent CTCAE Severity Grade	ITT Analysis Set
3.2.2.3	Serum Chemistry: Shift from Baseline by CTCAE Severity Grade	ITT Analysis Set
3.2.2.4	Summary of Transaminase Elevations	ITT Analysis Set
3.2.2.5	Time to Onset and Time to Resolution of Transaminase Elevations	ITT Analysis Set
3.2.3	Urinalysis: Summary of Actual Values at Baseline	ITT Analysis Set
3.2.4	Immunophenotyping Immunoglobulin and Serum protein electrophoresis (SPEP): Actual and Change from Baseline	ITT Analysis Set
3.2.5	Physical Examination	ITT Analysis Set
3.2.6	Palpable Lymphoma	ITT Analysis Set
3.2.7	Vital Signs: Actual and Change from Baseline	ITT Analysis Set
3.2.8	Vital Signs: Blood Pressure by Abnormal Status	ITT Analysis Set
3.2.9.1	12-Lead Electrocardiograms: Actual and Change from Baseline	ITT Analysis Set
3.2.9.2	12-Lead Electrocardiograms: Overall Results Shift From Baseline	ITT Analysis Set
3.2.9.3	12-Lead Electrocardiograms: QTc Interval and QTc Interval Change from Baseline	ITT Analysis Set
3.2.9.4	12-Lead Electrocardiograms: QTc Interval Shift from Baseline	ITT Analysis Set
3.3.1	IDEA Plasma Pharmacokinetic Concentration	PK Analysis Set
3.3.2	GS-563117 Plasma Pharmacokinetic Concentration	PK Analysis Set
3.3.3	PPD	
3.3.4	PPD	
3.3.5	PPD	
3.3.6	PPD

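### Table 3.2.4 and the mean-change plot pool IgM across all histologies, so a few LPL/WM subjects can dominate the mean IgM change

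*SAP*

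**What the plan says.** - **Table and analysis set.** The SAP table list (Section 13) has Table 3.2.4, "Immunophenotyping Immunoglobulin and Serum protein electrophoresis (SPEP): Actual and Change from Baseline", for the ITT analysis set. No version by disease is listed.
- **Who is in it.** Section 3.1.1 defines ITT by dosing alone: the "analysis set will comprise all subjects who receive" at least one dose of study drug. Section 1.2 admits four histologies, one of them "Lymphoplasmacytic lymphoma/Waldenstrom Macroglobulinemia (LPL/WM").
- **What is measured.** The Schedule of Assessments in Section 1.2 has a row "Serum immunoglobulins", repeated from Visit 2 onward, with no restriction by histology and no list of classes. It also has a row "SPEP (IgM monoclonal protein"). Footnote b reads "For subjects with LPL only, performed locally per standard of care". The footnote's marker is not visible in the text at hand, but SPEP is the evident match.
- **Statistics.** Section 7.2.1 states: "Descriptive statistics (sample size, mean, standard deviation, median, Q1, Q3, minimum and maximum) will be provided for each laboratory test". It also plans a plot of mean change from baseline over time for laboratory parameters.
- **Subsets.** Section 3.4 uses disease subcategory (FL, SLL, WM, MZL) for ORR, DOR, TTR and PFS only. The adverse-event subsets are sex, age, race and region. No subset is planned for laboratory data.

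**The concern.** The SAP itself treats IgM as the tumour protein in one histology. In LPL/WM subjects a fall in IgM is at least partly a treatment response. In the other subjects a fall would be read as a possible effect of the drug on immunoglobulins, which is a safety question. A single pooled mean adds the two together, and the WM values may lie on a much larger scale.

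Nothing else in the SAP clearly repairs this. Section 3.6 excludes no outliers. The allowance for log transformation or nonparametric methods in Section 3.7.1 is for efficacy endpoints. CTCAE grading in Section 7.2.3 covers hematology and serum biochemistry, and the table list has grade and shift tables only for those two. Table 3.2.4 is therefore the only visible tabular summary of immunoglobulins. At stake is how the mean IgM change, its SD and its plot are read in the study report.

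**Working it through.** The SAP states no figure on this point, so there is none to reproduce. The check asks how far a small WM group can move a pooled mean and a pooled median.

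**Input from the SAP:** 125 subjects enrolled (Section 1.3), all taken here as dosed and measured.

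**Assumed, because the SAP is silent:** IgM is reported; k = 1 to 20 WM subjects; WM baseline IgM b = 10 or 30 g/L with a 50% fall; mean change of -0.1 g/L in the others.

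**Formulas**
- Pooled mean change = [k × (-0.5b) + (125 - k) × (-0.1)] / 125
- WM share of that mean = k × (-0.5b) / [k × (-0.5b) + (125 - k) × (-0.1)]

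**Worked example, k = 3, b = 10:** WM sum = 3 × (-5) = -15; others' sum = 122 × (-0.1) = -12.2; pooled mean = -27.2/125 = -0.218 g/L; WM share = 15/27.2 = 55%.

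| WM subjects | WM baseline (g/L) | Pooled mean change (g/L) | WM share |
|---|---|---|---|
| 0 | – | -0.100 | 0% |
| 1 | 10 | -0.139 | 29% |
| 3 | 10 | -0.218 | 55% |
| 3 | 30 | -0.458 | 79% |
| 5 | 10 | -0.296 | 68% |
| 10 | 10 | -0.492 | 81% |
| 10 | 30 | -1.292 | 93% |

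If IgM does not change in the others, the WM share is 100% for any k of 1 or more.

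**SD.** Take 10 WM subjects changing by -15 g/L and 115 others by 0. The pooled mean is -150/125 = -1.20 g/L, and the SD is √[(10 × 13.8² + 115 × 1.2²)/124] = 4.09 g/L. All of it comes from the WM subjects.

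**Mean against median.** This was simulated with 4,000 replicates of 125 subjects. Non-WM change was normal with mean -0.1 and SD 0.2 g/L, and WM change was normal with mean -10 and SD 6 g/L.

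| WM subjects | Average pooled mean | Average pooled median |
|---|---|---|
| 3 | -0.337 | -0.105 |
| 5 | -0.495 | -0.109 |
| 10 | -0.891 | -0.119 |
| 20 | -1.689 | -0.143 |

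The true non-WM value is -0.10. The mean moves several-fold, while the median moves little when WM is a small minority.

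**Quartiles.** They still fall among non-WM subjects, but they are not wholly immune. With 10 WM subjects all below the rest, the pooled lower quartile sits at about (0.25 × 125 - 10)/115 = 18% of the non-WM distribution instead of 25%.

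**The case against.** The strongest reply is that the table already carries what a careful reader needs. Section 7.2.1 prints median, quartiles, minimum and maximum beside the mean, all laboratory data are listed (Section 7.2), and no decision hangs on the table. That largely stands. It limits the damage to the mean, the SD and the mean plot, and the plot has no median beside it.

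Four stronger readings are tempting, and the SAP does not support them:

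- **That the table cannot show the drug's effect on normal immunoglobulins.** The mechanism concerns IgM only. Any other class reported would not carry the tumour protein, and the SAP does not list the classes.
- **That a real IgM loss would be hidden.** Suppose 115 subjects at 0.7 g/L lose 30% (-0.21) and 10 WM subjects at 30 g/L rise by 10% (+3). The pooled mean is (30 - 24.15)/125 = +0.05 g/L, which looks like no loss. But the median and both quartiles are all -0.21, because WM is only 8% of subjects. The loss vanishes from the mean, not from the table.
- **That a misleading 95% CI is required.** Section 3.7 sets a general default that "will contain the following statistics: N (number in analysis set), n (number with data), mean, standard deviation (StD), 95% CI". Section 7.2.1 gives its own list for laboratory tests, and it contains no CI.
- **That SPEP is wrongly pooled over all ITT subjects.** If SPEP is collected only in LPL subjects, its statistics already come from them alone, and the number with data is printed. A label would help, but the numbers are not distorted.

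It is also fair to say that only the title of Table 3.2.4 is at hand. Rows by disease inside it cannot be ruled out, though nothing in the SAP plans them.

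**Conclusion.** The point holds for IgM and for the mean-based outputs. Followed as written, the SAP pools an analyte that it names as a tumour protein in one histology with the same analyte in all the others. Under the stated assumptions, three or more WM subjects at 10 g/L, or one at 30 g/L (15/27.4 = 55%), supply more than half of the pooled mean IgM change.

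The size depends on the number of LPL/WM subjects, their IgM levels and the change in the others, none of which the SAP gives. With no LPL/WM subjects enrolled, or IgM not reported, the problem disappears. It is a minor point: a cheap improvement to a descriptive safety summary, with no bearing on ORR.

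**What to change.** - In Table 3.2.4 and in the mean-change plot of Section 7.2.1, present IgM, and ideally all immunoglobulins, separately for LPL/WM subjects and for all other ITT subjects.
- Base any statement on IgM depletion on the non-LPL/WM column. The SAP does not establish that IgM is free of tumour protein in every FL, SLL or MZL subject, so this column is cleaner than the pooled one but not guaranteed pure.
- Label SPEP as LPL/WM only, with its own n.
- A pooled ITT column may stay as supplementary.

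The cost is a change to the table list and Section 7.2.1, and one extra column and plot line. Disease subcategory is already defined in Section 3.4, so no new data are needed. The LPL/WM column may be small and imprecise, and should be read as such.
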